10.11. Appendix 11: Abbreviations

The following is a list of abbreviations that may be used in the protocol.

Abbreviation	Term
A1 to A3	albuminuria (KDIGO albuminuria severity standardization)
Abs	absolute
ADL	activity/activities of daily living
ADME	absorption, distribution, metabolism, and excretion
AE	adverse event
AKI	acute kidney injury
ALT	alanine aminotransferase
AMS	accelerator mass spectrometer
API	active pharmaceutical ingredient
AST	aspartate aminotransferase
AUC	area under the curve
AUC ₂₄	area under the concentration-time curve over 24 hours
AUC _{inf}	area under the concentration-time curve to infinity
AUC _{last}	area under the plasma concentration-time profile from time zero to the time of the last quantifiable concentration
AUC _{tau}	area under the concentration-time curve at steady state over the dosing interval tau
AV	atrioventricular
AxMP	auxiliary medicinal product
BBS	Biospecimen Banking System
BCS	Biopharmaceutics Classification System
BID	twice a day
BMI	body mass index
BP	blood pressure
bpm	beats per minute
BUN	blood urea nitrogen
CFR	Code of Federal Regulations
CIOMS	Council for International Organizations of Medical Sciences
CK	creatinine kinase
CKD-EPI	chronic kidney disease epidemiology
CL	clearance
CL/F	apparent clearance of drug from plasma
C _{max}	maximum observed concentration
CO ₂	carbon dioxide (bicarbonate)
COVID-19	coronavirus disease 2019
CRF	case report form
CRO	contract research organization
CRU	clinical research unit
CSR	Clinical Study Report

Abbreviation	Term
CT	clinical trial
CTIS	Clinical Trial Information System
CYP	cytochrome P450
DCT	data collection tool
DDI	drug-drug interaction
DICI	drug-induced creatinine increase
DIKI	drug-induced kidney injury
DILI	drug-induced liver injury
dn	dose-normalized
EC	ethics committee
ECC	emergency contact card
ECG	electrocardiogram or electrocardiography
eCrCl	estimated creatinine clearance
eCRF	electronic case report form
EDB	exposure during breastfeeding
E-DMC	External Data Monitoring Committee
EDP	exposure during pregnancy
EDR	extemporaneous dispensing record
EFD	embryo-fetal development
eGFR	estimated glomerular filtration rate
eSAE	electronic serious adverse event
ET	early termination
EU	European Union
EudraCT	European Union Drug Regulating Authorities Clinical Trials (European Clinical Trials Database)
F	absolute oral bioavailability
F _a	fraction of dose absorbed
FDA	Food and Drug Administration
F _g	fraction escaping gut metabolism
F _h	fraction escaping hepatic first-pass elimination
FU	follow-up
GCP	Good Clinical Practice
GGT	gamma-glutamyl transferase
GLP-1	glucagon-like peptide-1
GLP-1R	glucagon-like peptide-1 receptor
HBcAb	hepatitis B core antibody
HBsAb	hepatitis B surface antibody
HBsAg	hepatitis B surface antigen
HCVA _b	hepatitis C antibody
HIV	human immunodeficiency virus
HR	heart rate
IB	Investigator's Brochure

Abbreviation	Term
ICD	informed consent document
ICH	International Council for Harmonisation of Technical Requirements for Pharmaceuticals for Human Use
ID	identification
IMP	investigational medicinal product
IND	Investigational New Drug
INR	international normalized ratio
IRB	Institutional Review Board
IV	intravenous(ly)
K ₂ EDTA	dipotassium ethylenediaminetetraacetic acid
KDIGO	Kidney Disease Improving Global Outcomes
LBBB	left bundle branch block
LC/MS/MS	liquid chromatography tandem mass spectrometric method
LFT	liver function test
MCH	mean corpuscular hemoglobin
MCHC	mean corpuscular hemoglobin concentration
MCV	mean corpuscular volume
MEN2	multiple endocrine neoplasia type 2
MIST	Metabolites in Safety Testing
MQI	medically qualified individual
MRT	mean residence time
MTC	medullary thyroid carcinoma
NA	not applicable
NIMP	noninvestigational medicinal product
NOAEL	no-observed-adverse-effect level
OATP	organic anion transporting polypeptide
PD	protocol deviation
PE	physical exam
PK	pharmacokinetic(s)
PO	oral(ly)
PPI	proton pump inhibitor
PSSA	Pfizer's Serious Adverse Event Submission Assistant
PT	prothrombin time
PVC	premature ventricular contraction/complex
QD	once daily
QP	qualified person
QTc	corrected QT interval
QTcF	QTc corrected using Fridericia's formula
qual	qualitative
RBC	red blood cell
SAE	serious adverse event
SAI	site administration instructions

Abbreviation	Term
SAP	Statistical Analysis Plan
SARS-CoV-2	severe acute respiratory syndrome coronavirus 2
Scr	serum creatinine
Scys	serum cystatin C
SoA	schedule of activities
SOC	system organ class
SOP	standard operating procedure
SRSD	Single Reference Safety Document
SSID	study-specific participant identification
SUSAR	Suspected Unexpected Serious Adverse Reaction
$t_{1/2}$	plasma elimination half life
T2DM	type 2 diabetes mellitus
TA	Technical Agreement
T bili	total bilirubin
TEAE	treatment-emergent adverse event
THC	tetrahydrocannabinol
T_{max}	time to reach C_{max}
UACR	urine albumin/creatinine ratio
UGT	uridine 5'-diphospho-glucuronosyltransferase
ULN	upper limit of normal
UPLC-HRMS	ultra-high performance liquid chromatography coupled high resolution mass spectrometry
US	United States
V_{ss}	steady-state volume of distribution
V_z/F	apparent volume of distribution
WBA	whole body autoradiography
WBC	white blood cell
XTC	ecstasy

1. VERSION HISTORY

Table 1. Summary of Changes

Version/ Date	Associated Protocol Amendment	Rationale	Specific Changes
1 11 Jan 2023	Original 30 Sep 2022	N/A	N/A

2. INTRODUCTION

The purpose of the study is to assess the metabolism and extent of excretion of [¹⁴C]PF-07081532 in urine and feces, following oral administration, in the fed state, in healthy male participants. This information will enable assessment of clearance mechanisms of PF-07081532 as well as identify disproportionate metabolites that should be qualified to adhere to the ICH M3 (R2) MIST guidance. In addition, this study will characterize the fraction of dose absorbed and the bioavailability of orally administered PF-07081532 in the fed state, in reference to an IV dose of [¹⁴C]PF-07081532, while it will also assess PK parameters following both oral and IV administration of [¹⁴C]PF-07081532.

This statistical analysis plan (SAP) provides the detailed methodology for summary and statistical analyses of the data collected in Study C3991006.

2.1. Modifications to the Analysis Plan Described in the Protocol

Not Applicable

2.2. Study Objectives, Endpoints, and Estimands

Type	Objective	Endpoints
Primary		
PK Section 6.1.1	
 To characterize the extent of excretion of total radioactivity in urine, feces, and emesis (if any) following administration of a single oral dose of [¹⁴C]PF-07081532. 	
 Total recovery of radioactivity in urine, feces, and emesis (if any), and both routes combined, expressed as a percent of total oral radioactive dose administered.
PK Section 6.1.2	
 To characterize the metabolic profile and identify circulating and excreted metabolites following administration of a single oral dose of [¹⁴C]PF-07081532. 	
 Metabolic profiling/identification and determination of relative abundance of [¹⁴C]PF-07081532 and the metabolites of [¹⁴C]PF-07081532 in plasma, urine, and feces.
Secondary		
PK Section 6.2.1	
 To quantify plasma PK parameters of PF-07081532 and total radioactivity following administration of a single oral dose of [¹⁴C]PF-07081532. 	
 AUC_{last}, C_{max}, T_{max}, and if data permit, AUC_{inf}, $t_{1/2}$, CL/F (PF-07081532 only), and Vz/F (PF-07081532 only), to describe single oral dose PK in Period 1 of: Total radioactivity in plasma; PF-07081532 in plasma.
PK Section 6.2.1	
 To quantify plasma PK parameters of [¹⁴C]PF-07081532, following administration of a single, IV, microdose of [¹⁴C]PF-07081532. 	
 [¹⁴C]PF-07081532 parameters to describe IV plasma PK: AUC_{last}, $AUC_{last}(dn)$, C_{max}, $C_{max}(dn)$, T_{max}, and if data permit, AUC_{inf}, $AUC_{inf}(dn)$, $t_{1/2}$, CL, V_{ss} and MRT.

[figure not shown]
PK Section 6.2.2	
 To determine the absolute oral bioavailability (F) of PF-07081532 following administration of a single oral dose of PF-07081532 compared to a single IV microdose of [^{14}C]PF-07081532. 	
 F computed from plasma AUC_{inf} (if data permit, otherwise AUC_{last}) of oral unlabeled PF-07081532 in Period 2 and IV microdose of [^{14}C]PF-07081532 in Period 2.
PK Section 6.2.3	
 To determine the fraction of dose absorbed (F_a) following administration of a single oral dose of [^{14}C]PF-07081532. 	
 F_a calculated from ratio of total urinary radioactivity following oral administration of [^{14}C]PF-07081532 in Period 1 and IV administration of [^{14}C]PF-07081532 in Period 2.
Safety Section 6.6	
 To evaluate safety and tolerability of PF-07081532, administered as a single oral dose of [^{14}C]PF-07081532 or a single oral dose of PF-07081532 followed by administration of a single IV microdose of [^{14}C]PF-07081532. 	
 Safety endpoints including physical examinations, adverse events, clinical laboratory measurements, vital signs, and ECG.
Tertiary/Exploratory:		
PK Section 6.3.1	
 To characterize cumulative rate of excretion of total radioactivity in urine and feces over time following administration of a single oral dose of [^{14}C]PF-07081532. 	
 Cumulative recovery of radioactivity in urine and feces, and both routes combined over time as a percentage of total radioactive dose administered.
PK Section 6.3.2	
 To quantify plasma PK parameters of PF-07081532, following administration of a single oral dose of (unlabeled) PF-07081532. 	
 Parameters to describe oral plasma PK following oral administration of PF-07081532 in Period 2: C_{max}, $C_{\text{max}}(\text{dn})$, T_{max}, AUC_{last}, $\text{AUC}_{\text{last}}(\text{dn})$, and if data permit, AUC_{inf}, $\text{AUC}_{\text{inf}}(\text{dn})$, $t_{1/2}$, CL/F and V_{z}/F.
Other Section 6.3.3	CCI	
Other Section 6.3.4		

There are no estimands for this study.

2.3. Study Design

C3991006 is a Phase 1, open-label, 2-period, fixed sequence study to characterize the metabolic profile and routes of excretion of oral [^{14}C]PF-07081532 and to evaluate the absolute oral bioavailability (F) and fraction absorbed (F_a) of PF-07081532 in healthy male participants.

Participants will be screened for enrollment in this study within 28 days of dosing on Day 1 of **Period 1**, to confirm that they meet the inclusion/exclusion criteria specified in Section 5 of the protocol. The expected duration of participation from screening to follow-up will be approximately 8 weeks (minimum) to approximately 12 weeks (maximum). The overall study design is summarized in the schema below.

- a. See Section 4.1 of the protocol for details on Period 1 discharge criteria.
- b. At least 21 days of washout is required between dosing in Period 1 and Period 2.
- c. In Period 2, participants will be discharged from the CRU on Day 7.

Regimen in Period 1: An oral dose of 30 mg PF-07081532 containing approximately 250 nCi [¹⁴C] (ie, radiolabeled PF-07081532, [¹⁴C]PF-07081532) will be administered within approximately 10 minutes of completion of a standard breakfast.

Regimen in Period 2: An oral dose of 30 mg unlabeled PF-07081532 will be administered followed at approximate T_{max} by an IV dose of 250 nCi [¹⁴C] in 100 μ g of PF-07081532 (ie, [¹⁴C]PF-07081532). The [¹⁴C]PF-07081532 IV dose will be administered as an infusion over approximately 15 minutes, starting at approximately 1 hour (T_{max}) after the administration of the oral unlabeled PF-07081532 dose. Oral unlabeled PF-07081532 will be administered within approximately 10 minutes of completion of a standard breakfast.

In Period 1, a sufficient number of participants will be admitted on Day -1 to the CRU to ensure that 6 participants are dosed on Day 1. Any participants who are prematurely withdrawn (or offer non-evaluable or partially evaluable data) will be replaced to ensure 6 evaluable participants completing Period 1. In Period 2, participants who are prematurely withdrawn may be replaced at the discretion of sponsor.

3. ENDPOINTS AND BASELINE VARIABLES: DEFINITIONS AND CONVENTIONS

3.1. Primary Endpoint(s)

Urine, feces and vomitus samples will be collected according to the Schedule of Activities given in the protocol and will be analyzed for total radioactivity.

3.1.1. Extent of Excretion (Period 1 Only)

Urine, feces and vomitus samples will be collected according to the Schedule of Activities given in the protocol and will be analyzed for total radioactivity.

Extent of Excretion will be determined by recovery of total radioactivity excreted in urine and feces (and emesis, if applicable). Total recovery of radioactivity in urine and feces, and both routes combined, will be calculated as a percent of total oral radioactive dose administered. The percentage of the administered radioactivity excreted at each time interval and the total percent of dose excreted in urine and feces will be reported whenever possible.

Note: the extent of Excretion analysis is summarized in this SAP for completeness only. Methods and results related to extent of Excretion will be detailed in a separate report and will be summarized within the Clinical Study Report (CSR).

3.1.2. Metabolite Endpoints

Plasma, urine and fecal samples collected in Period 1 will be analyzed for metabolites of PF-07081532. Major metabolites of PF-07081532 in plasma, urine and feces may be identified if possible. Contributions of parent and each major metabolite to total radioactivity recovered in urine and feces and to circulating radioactivity in plasma will be quantified.

Results of the metabolic profiling analysis will be detailed in a separate report and will be summarized within the CSR.

Note: Methods and results related to analysis of metabolites will similarly be detailed in a separate report provided by TNO.

3.2. Secondary Endpoint(s)

3.2.1. Plasma Pharmacokinetic Parameters

Plasma samples for PK analysis will be collected according to the Schedule of Activities given in the protocol.

- *For Period 1, following a single oral administration of [¹⁴C]PF-07081532, oral PK parameters for total [¹⁴C] radioactivity will be derived from the concentration equivalent-time profiles, where appropriate. Additionally, PK parameters for PF-07081532 will be derived from the concentration-time profiles based on LC/MS/MS analysis of plasma samples.*
- *For Period 2, following a single oral dose of unlabeled PF-07081532, PK parameters for PF-07081532 will be derived from the concentration-time profiles based on LC/MS/MS analysis of plasma samples (note that this reflects a tertiary endpoint and as such is also listed under [Section 3.3](#)).*
- *For Period 2, following a single IV microdose dose of [¹⁴C]PF-07081532 at 1 hour post oral dose, IV plasma PK parameters of [¹⁴C]PF-07081532 will be derived from plasma radioactivity concentration-time profiles following chromatographic separation of [¹⁴C]PF-07081532.*

The following plasma PK parameters will be determined using standard non-compartmental methods:

Table 2. Summary of plasma PK Parameters to be calculated

Parameter	Analysis Scale	After oral dose of [¹⁴ C]PF-07081532 (Period 1)		After IV dose of [¹⁴ C]PF-07081532 (Period 2)	
		Total Radioactivity	PF-07081532	[¹⁴ C]PF-07081532	PF-07081532
AUC _{1as1}	ln	D	D	D	D
AUC _{1as1} (dn)	ln	NC	NC	D	D
AUC _{inf*}	ln	D	D	D	D
AUC _{inf*(dn)}	ln	NC	NC	D	D
C _{max}	ln	D	D	D	D
C _{max,ldn}	ln	NC	NC	D	D
T _{max}	R	D	D	D	D
t _{1/2*}	R	D	D	D	D
CL*	ln	NC	NC	D	NC
V..*	ln	NC	NC	D	NC
MRT*	ln	NC	NC	D	NC
CL/F*	ln	NC	D	NC	D
V _z /F*	ln	NC	D	NC	D

*=if data permits. Abbreviations: D=displayed with descriptive statistics as outlined in Table 3 in [Section 6.2.1](#); dn=dose normalized; ln=natural-log transformed; NC= not calculated; R=raw (untransformed);

Actual PK sampling times will be used in the derivation of PK parameters, defined relative to the time of the oral dose for the parameters referring to oral dosing and relative to the start of the 15-minute IV infusion for the parameters referring to IV dosing. Actual administered [¹⁴C] doses will be used for the total [¹⁴C] radioactivity and [¹⁴C]PF-07081532 PK parameter calculations.

Plasma PK parameters above will be listed and summarized descriptively as appropriate, by analyte (total [¹⁴C], unlabeled PF-07081532, and [¹⁴C]PF-07081532) and route of administration (oral or IV), as specified in [Section 5.2](#)

Absolute bioavailability (F) will additionally be calculated as the ratio of adjusted geometric means of dose-normalized AUC_{inf} (if data permit, otherwise AUC_{1ast(dn)}) following oral, unlabeled, PF-07081532 and intravenous, [¹⁴C]PF-07081532 which is equivalent to the following equation:

$$F = [\text{PF-07081532}_\text{AUCpJPF-07081532}_\text{AUC;v} * [\text{PF-07081532}_\text{Dose;v}/\text{PF-07081532}_\text{Dosepo}]$$

3.2.2. Urine Pharmacokinetic Parameter

The following urine parameters will be calculated following single dose administration of a microtracer dose of [¹⁴C]PF-07081532 (oral and IV administration), as data permit.

Residual [¹⁴C] levels from Period 1 will be accounted for using an appropriate method, based on AMS principles and methodology.

Parameter	Definition	Method of Determination
Total [¹⁴ C]_Urine_PO	Total cumulative radioactivity excreted into urine from time zero up to the time of last measurable concentration following oral administration of [¹⁴ C]PF-07081532 (Period 1 only)	Directly from observed [¹⁴ C] data, calculated as sum of [¹⁴ C urine concentration × sample volume] for each collection interval
Total [¹⁴ C]_Urine_PO_Trunc*	Total cumulative radioactivity excreted into urine from time zero up to Day 7 (matching duration of Period 2 urine collection up to discharge) following oral administration of [¹⁴ C]PF-07081532 (Period 1 only)	Directly from observed [¹⁴ C] data, calculated as sum of [¹⁴ C urine concentration × sample volume] for each collection interval
Total [¹⁴ C]_Urine_IV	Total cumulative radioactivity excreted into urine from time zero up to the time of last measurable concentration following IV administered [¹⁴ C]PF-07081532 microdose (Period 2 only)	Directly from observed [¹⁴ C] data, calculated as sum of [¹⁴ C urine concentration × sample volume] for each collection interval
% [¹⁴ C]_Urine_PO	% of radioactivity in the urine following oral administration, expressed as a percent of the radioactive dose administered (Period 1 only)	(Total [¹⁴ C]_Urine_PO/[¹⁴ C] Dose _{po}) *100 where, [¹⁴ C] Dose _{po} is orally administered actual dose of [¹⁴ C]PF-07081532
% [¹⁴ C]_Urine_PO_Trunc*	% of radioactivity in the urine up to Day 7 (matching duration of Period 2 urine collection up to discharge) following oral administration, expressed as a percent of the radioactive dose administered (Period 1 only)	(Total [¹⁴ C]_Urine_PO_Trunc/[¹⁴ C] Dose _{po}) *100 where, [¹⁴ C] Dose _{po} is orally administered actual dose of [¹⁴ C]PF-07081532
% [¹⁴ C]_Urine_IV	% of radioactivity in the urine following IV administration expressed as a percent of the radioactive dose administered (Period 2 only)	(Total [¹⁴ C]_Urine_IV/[¹⁴ C] Dose _{iv}) *100 where, [¹⁴ C] Dose _{iv} is [¹⁴ C] IV administered actual dose of [¹⁴ C]PF-07081532

* _Trunc parameters may not be calculated and reported if not applicable (ie, no participant is discharged after Day 7 in Period 1).

*F_a will be estimated as the ratio of adjusted geometric means of the % of administered radioactive dose excreted into urine following oral and IV administration of [¹⁴C]PF-07081532 in **Periods 1 and 2**, respectively.*

Urine radioactivity up to Day 7 will be used for Period 1 to match the duration of Period 2 urine collection up to discharge:

$$F_a = [\% [^{14}\text{C}] \text{ Urine PO Trunc} / \% [^{14}\text{C}] \text{ Urine IV}]$$

For IV administration of $[^{14}\text{C}]$ PF-07081532, the weight of dose administered and solution density, in conjunction with the dosing solution concentration data will be used to determine the exact dose administered, where formulas will be included in the analysis and reporting plans. This actual dose will be used for PK parameter calculations.

For oral administration of $[^{14}\text{C}]$ PF-07081532, the weight of drug powders added to each individual dosing container will be used along with specific activity and chiral potency of the drug powder to determine exact dose administered, where formulas will be included in the analysis and reporting plans. This actual dose will be used for PK parameter calculations.

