6.2.1. Preparation and Dispensing

Within this protocol, preparation refers to the investigator site activities performed to make the study intervention ready for administration or dispensing to the participant by qualified staff. Dispensing is defined as the provision of study intervention, concomitant treatments, and accompanying information by qualified staff member(s) to a healthcare provider, participant in accordance with this protocol. Local health authority regulations or investigator site guidelines may use alternative terms for these activities.

Unlabeled PF-07081532 and [¹⁴C]PF-07081532 oral dosing formulations will be prepared in the CRU by 2 trained personnel and QP. Details of dose preparation will be given in a separate EDR. The prepared doses will be provided in unit dose containers and labeled in accordance with Pfizer regulations and the investigator site's labeling requirements.

[¹⁴C]PF-07081532 formulation for IV administration will be manufactured at the CRU by 2 trained personnel and QP-released prior to administration. Details of the dose preparation will be provided in a separate TA. The prepared doses will be provided in unit dose containers and labeled in accordance with Pfizer regulations and the investigator site's labeling requirements.

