6.5. Study Intervention Compliance

When the individual dose for a participant is prepared from a bulk supply, the preparation of the dose will be confirmed by a second qualified member of the study site staff.

When participants are dosed at the site, they will receive study intervention directly from the investigator or designee, under medical supervision. The date and time of each dose administered in the clinic will be recorded in the source documents and recorded in the CRF. The dose of study intervention and study participant identification will be confirmed at the time of dosing by a member of the study site staff other than the person administering the study intervention. Study site personnel will examine each participant's mouth to ensure that the oral dose of study intervention was ingested.

See the site administration instructions for instructions on how to prepare the study intervention for administration. Study intervention should be prepared and dispensed by an appropriately qualified and experienced member of the study staff (eg, physician, nurse, physician's assistant, nurse practitioner, pharmacy assistant/technician, or pharmacist) as allowed by local, state, and institutional guidance.

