8.5.6. Analysis of Dosing Formulation and Determination of Administered Dose

Detailed storage and shipment procedures will be provided in the SAI and laboratory manual to the clinical site prior to the start of the clinical trial.

For IV administration of [¹⁴C]PF-07081532, the dose volume administered to individual participants will be controlled using pre-calibrated infusion pumps. Volume of IV dose (computed using weight of the dosing solution administered and the density of the dosing solutions), and concentration of PF-07081532 and radioactivity in dosing solution will be used to determine the exact dose administered for each participant.

The actual doses administered will be recorded in the CRF and will be used for calculating PK parameters as described in [Section 8.10](#).

Details on administration of dose and amount of doses administered in Period 1 and Period 2 will be described in the SAI and the laboratory manual.

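### Does the oral [14C] dose in SAP 3.2.2 need a correction for liquid left in the dosing container?

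*SAP*

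**What the plan says.** SAP 3.2.2 expresses urinary radioactivity after oral dosing as a percentage of the oral [14C] dose, whose definition reads "is orally administered actual dose of [¹⁴ C]PF-07081532". Fa is the ratio of that percentage, cut at Day 7 of Period 1, to the matching IV percentage from Period 2.

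The same section says how each dose is found. The IV dose is built from the weighed amount delivered, the density of the solution and its measured concentration. For oral, the sentence reads "the weight of drug powders added to each individual dosing container will be used along with specific activity"; chiral potency is the third input. Both sentences carry the same rider: "where formulas will be included in the analysis and reporting plans".

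Protocol 8.5.6 states that "The actual doses administered will be recorded in the CRF and will be used for calculating PK parameters". It describes the exact-dose calculation for IV only, and then says that details of administration and the "amount of doses administered in Period 1 and Period 2 will be described in the SAI and the laboratory manual". On oral preparation, Protocol 6.2.1 says: "Details of dose preparation will be given in a separate EDR". Protocol 6.5 has staff examine each participant's "mouth to ensure that the oral dose of study intervention was ingested".

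**The concern.** The oral dose is a liquid, and some of it can cling to the container. Powder weight, specific activity and potency are all known before dosing, so none of them can register what was left behind. The mouth check confirms swallowing; it does not measure residue. The readable text of the two documents mentions no rinse, weigh-back or residue assay for the oral dose.

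The two sides of the Fa ratio therefore look unequal: a loaded amount under the oral percentage and a delivered amount under the IV percentage. Any residue would push Fa down, it would not cancel, and the 90% confidence interval would not reveal it. If the separate excretion report used the same loaded dose, total recovery, a primary endpoint, would be low by the same factor. The Period 1 discharge criteria are also percentages of the radioactive dose.

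**Working it through.** The plan states no residue and no residue-corrected figure, so there is nothing of its own to reproduce. The check asks how large the effect could be under stated assumptions.

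**Inputs.** Nominal oral activity 250 nCi (Protocol 6.1.1); 6 participants (Protocol 9.5); log-scale mixed model with a 90% interval (SAP 5.2.3), which for complete pairs equals a paired analysis with 5 degrees of freedom. Assumed, because the documents do not give them: residue r of 1%, 3% and 5%, and an SD of the within-participant log difference of 0.05 to 0.30.

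**Size of the shift.** Let L be the activity loaded and U the activity in urine. The swallowed dose is L(1-r).

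- Reported percentage = 100U/L. True percentage = 100U/[L(1-r)]. Reported/true = 1-r.
- The IV term has no counterpart, so reported Fa = true Fa × (1-r).
- Residue of 1%, 3%, 5% is 2.5, 7.5, 12.5 nCi of 250. A true Fa of 1.00 reads 0.99, 0.97, 0.95.

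In a simulated six-pair data set, r = 5% throughout moved the estimate and limits from 0.915 (0.891, 0.941) to 0.870 (0.846, 0.894), each exactly 0.95 times its former value. With r of 1, 2, 3, 5, 8 and 10% across the six, the estimate was multiplied by the geometric mean of (1-r), 0.951.

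**Shift against precision.** Half-width on the log scale = 2.015 × SD/√6. Coverage of the nominal 90% interval comes from a noncentral t with 5 degrees of freedom and noncentrality ln(1-r) × √6/SD.

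| SD | Half-width | Coverage, r = 1% | r = 3% | r = 5% |
|---|---|---|---|---|
| 0.05 | 0.041 | 0.869 | 0.637 | 0.304 |
| 0.10 | 0.082 | 0.892 | 0.830 | 0.708 |
| 0.20 | 0.165 | 0.898 | 0.882 | 0.850 |
| 0.30 | 0.247 | 0.899 | 0.892 | 0.878 |

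At r = 1% the loss is at most about 3 percentage points (0.90 to 0.869). Poor coverage needs both a residue of several percent in every participant and very low variability.

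**Discharge criteria (Protocol 4.1).** If the check used the loaded dose, both percentage criteria would move, in opposite directions:

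- Criterion 1, at least 90% recovered: 0.90/(1-r) = 90.9%, 92.8%, 94.7% of the swallowed dose, so met later.
- Criterion 2, under 1% per 24 hours: 1%/(1-r) = 1.01%, 1.03%, 1.05% of the swallowed dose, so met slightly earlier.

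The net effect on length of stay is not determined. Discharge cannot come before Day 7 and Fa uses Period 1 urine only to Day 7, so the discharge date does not feed into Fa.

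**What the text commits to.** The definition of the denominator and Protocol 8.5.6 both require the administered dose. The oral sentence in SAP 3.2.2 lists inputs that will be used; it does not say that they are the only ones, and it places the formula in another document. A formula that ignored material residue would conflict with the SAP's own definition.

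**The case for a change.** The best case for a change is that the SAP defers the formula but names the inputs itself, and those inputs alone reach the stated target only if residue is zero or handled separately. The IV sentence shows that the authors knew how to specify a delivered dose. The error would run in one direction, so averaging over participants would not remove it. It would also be irrecoverable if emptied containers were thrown away unmeasured. The remedy would be cheap: one sentence or citation and roughly six container measurements.

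Much of this stands. The named inputs give a loaded amount, the factor (1-r) is exact for a common r, and neither document tells the reader how residue is handled. What does not follow is that the plan would produce a wrong dose. Rinsing the container, having the participant swallow the rinse, or weighing the emptied container are dosing-room procedures, and both documents say where such detail is kept. Those documents are not available here, so their silence cannot be assumed. Requiring a measured subtraction would also go too far, since a swallowed rinse that leaves little behind makes the correction negligible.

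**Conclusion.** No change to the plan is called for. The quantity the SAP asks for is the right one, and the step from loaded to swallowed activity is operational detail assigned to the analysis and reporting plans, the SAI and the laboratory manual. An analyst following the stated definition would account for residue if it mattered.

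If it were wholly ignored, Fa and the oral urine percentages would be multiplied by (1-r), which is 0.99 to 0.95 for an assumed r of 1% to 5%. Total recovery would shift likewise only if the separate excretion report used the same loaded dose; SAP 6.1.1 says it rests on the dose administered. Neither r nor the variability of Fa appears in the documents, so the coverage figures show what could happen and are no evidence that it will. No hypothesis is tested, Fa is a secondary endpoint, Protocol 2.1 sets no numerical threshold for the BCS classification, and no conclusion is shown to change. A cross-reference from SAP 3.2.2 to the place where residue is handled would help a reader, but the analysis does not depend on it.
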